Describe how data will be managed after the study is complete:

- If data/specimens will be maintained, specify whether identifiers will be removed from the maintained information/material.
- If identifiers will not be removed, provide justification for retaining them and describe how you will protect confidentiality.
- If the data/specimens will be destroyed, verify that this will not violate retention policies and will adhere to applicable facility

requirements.

66767 CLOSED

If applicable, describe procedures for sharing data/specimens with collaborators not affiliated with UK.

For additional considerations: Return of Research Results or Incidental Research Findings HIPAA policies FERPA policies Procedures for Transfer agreements Information regarding multi-site studies NIH Genomic Data Sharing (GDS) Policy Digital Data

Video recordings will be collected of all intervention sessions, and audio recordings will be collected of focus group sessions. These will be recorded using Zoom platform and saved on a secure share drive maintained by Sanders-Brown Center on Aging. This recordings will be used to validate the fidelity of the study intervention among interventionists (occupational therapists). Existing records of PHI will be used for recruitment purposes to identify eligible participants from the Kentucky Neuroscience Institute and the Sanders-Brown Center on Aging Iongitudinal cohorts.

All materials, except behavior journals, will be in electronic format. All data will be uploaded and saved to REDCap the day of acquisition from participants. Hard copies of behavior journals will be electronically scanned with 48 hours of receipt and destroyed via shredding following uploading to REDCap. All hard copies (behavior journals and paper copies of consent forms) will be stored at the Sanders-Brown Center on Aging Clinic at the stored and saved to REDCap.

building, office, and cabinet will be locked at all times of non-use. REDCap is a password-protected, secure data management web application in the secure data center run by the Institute for Pharmaceutical Outcomes and Policy (IPOP) physically located in the new Biological and Pharmaceutical Complex building at the University of Kentucky. The files will be stored for a period of six years and destroyed per UK Policy A13-050. Digital audio recordings and electronic transcription of all interviews will be obtained. These electronic files will also be stored on REDCap.

Upon enrollment in the study, subjects will be given pseudonyms to protect confidentiality and de-identify data. Each participant will be assigned a participant number and pseudonym, which will be used to identify the person during data analysis and when managing data. This de-identified human subject data will be stored on REDCap. Records maintained by SBCoA are not UK medical records, and so PHI and PII will not be used. At the conclusion of the study, all individual data stored on REDCap, a secure location, for a period of 6 years, after which deletion of electronic files will destroy it. All video recording/electronic data will be stored for a period of six years after which files will be destroyed using the University of Kentucky's Policy for Reuse and Disposal of Electronic Media. UK Healthcare Policy and Procedure A13-050 states "all electronic media shall be erased (i.e. purged) using data overwriting software that conforms to the requirements stated in NIST SP800-88." IRB research records (approved IRB protocol, Form K, signed consent documents etc.) will be maintained for 6 years after study closure per the study closure SOP.

Confidentiality will be maintained, however, in the case in which abuse or concern of participants' safety, the researcher is required by law to report to authorities.

NIH Data and Resources Sharing Plan

This pilot project will include data from a community-based sample of 40 informal caregivers of persons living with moderate to severe dementia. In line with the official protocol of the Roybal Translational Research Center to Promote Context-Specific Caregiving Mastery for Informal Caregivers of Community-Dwelling Persons Living with Alzheimer's Disease at Emory University, the dataset will include common measures of caregiver self-efficacy and mastery developed by Perlin and colleagues as well as certain demographic data. These data will be deposited in the Center data repository and stored in Planeton and the context at the second seco

the University of Kentucky. Data from this pilot study will be available to qualified researchers through a data sharing agreement that is fully consistent with NIH data sharing policies and applicable laws and regulations as well as official policies and practices established by the Roybal Center at Emory. These data will be made available no later than the on-line publication date of the main findings from the final dataset.

Following our IRB protocol, each participant, will be assigned a participant number and pseudonym upon enrollment in the study, which will be used to identify the person during data analysis and when managing data. All data will be uploaded and saved to REDCap the day of acquisition from participants. REDCap is a password-protected, secure data management web application in the secure data center run by the Institute for Pharmaceutical Outcomes and Policy (IPOP) physically located in the new Biological and Pharmaceutical Complex building at the University of Kentucky. Although these data will be de-identified prior to release for sharing, there remains a possibility of deductive disclosure of participants with unusual characteristics. Therefore, this data sharing agreement will require: 1) a commitment only to use the data for research purposes and not to identify any individual participant; 2) a commitment to securing the data using appropriate computer technology; and 3) a commitment to destroy or return the data after analyses are completed. Protections against breach of confidentiality of data:

Upon enrollment in the study, each participant will be assigned a participant number and pseudonym, which will be used to identify the person during data analysis and when managing data. All data will be uploaded and saved to REDCap the day of acquisition from participants. REDCap is a password-protected, secure data management web application in the secure data center run by the Institute for Pharmaceutical Outcomes and Policy (IPOP) physically located in the new Biological and Pharmaceutical Complex building at the University of Kentucky. The files will be stored for a period of six years and destroyed according to UK Policy A13-050. Digital video/audio recordings and electronic transcription of all study sessions and audio recording of focus groups will be obtained using Zoom platform. These electronic files will also be stored on on a secure share drive developed and maintained by the UK Sanders-Brown Center on Aging (Complex Digital U). Confidentiality will be maintained; however, in the case in which abuse or concern of participants' safety, the researcher is required by law to report to authorities.

Protection regarding possible risks of environmental modifications:

66767 CLOSED

UK IRB policies state that IRB-related research records must be retained for a minimum of 6 years after study closure. Do you confirm that you will retain all IRB-related records for a minimum of 6 years after study closure? • Yes < No

Payment

Describe the incentives (monetary or other) being offered to subjects for their participation. If monetary compensation is offered, indicate the amount and describe the terms and schedule of payment. Please review this guidance for more information on payments to subjects, including restrictions and expectations.

Participants will not receive any monetary compensation.

Costs to Subjects

Include a list of services and/or tests that will not be paid for by the sponsor and/or the study (e.g., MRI, HIV). Keep in mind that a subject will not know what is "standard" – and thus not covered by the sponsor/study – unless you tell them.

There are no costs associated with taking part in this study.

Data and Safety Monitoring

The IRB requires review and approval of data and safety monitoring plans for greater than minimal risk research or NIH-funded/FDAregulated clinical investigations.

- If you are conducting greater than minimal risk research, or your clinical investigation is NIH-funded, describe your Data and Safety Monitoring Plan (DSMP). Click here for additional guidance on developing a Data and Safety Monitoring Plan.
- If this is a non-sponsored investigator-initiated protocol considered greater than minimal risk research, and if you are planning on using a Data and Safety Monitoring Board (DSMB) as part of your DSMP, click here for additional guidance for information to include with your IRB application.

0

We have attached our data safety monitoring plan in the attachment section of this application.

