This study will utilize a one-arm, pre/post design. Forty people living with dementia with behavioral disturbance and their primary care partner will receive the H@H intervention (total n=80), a 6-week telehealth intervention delivered by an occupational therapist during weekly visits. Focus groups before and after the intervention with caregiver informants, interventionists, and study facilitators will allow opportunity to refine the intervention specific to the needs of caregivers in rural Appalachia. Caregivers of community-residing persons living with dementia with complaints of behavioral disturbance will be recruited for this project. The University of Kentucky Alzheimer's Disease Research Center and the Kentucky Neuroscience Institute have established contacts throughout the rural Appalachian region which provides access to our targeted population.

Attachments

Subject Recruitment Methods & Advertising

Describe how the study team will identify and recruit subjects. Please consider the following items and provide additional information as needed so that the IRB can follow each step of the recruitment process.

- How will the study team identify potential participants?
- Who will first contact the potential subjects, and how?
- Will you use advertisements? If so, how will you distribute those?
- · How and where will the research team meet with potential participants?
- If applicable, describe proposed outreach programs for recruiting women, minorities, or disparate populations.
- How you will minimize undue influence in recruitment?
- Attach copies of all recruiting and advertising materials (emails, verbal scripts, flyers, posts, messages, etc.).

For additional information on recruiting and advertising:

- IRB Application Instructions Advertisements
- PI Guide to Identification and Recruitment of Human Subjects for Research

This project, located at the University of Kentucky (UK) will use established cohorts, networks, and patient-groups for recruitment. UK is a leading healthcare center for neurology care in the state of Kentucky. UK also has well-established community partnerships and networks within rural, Appalachia Kentucky.

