Each caregiver will complete the 6-week Harmony at HOME telehealth intervention:

Select participants will engage in focus groups prior to and following the intervention with caregiver informants, clinicians, and study facilitators. Participants will be selected based on enrollment and willingness to participant The first 10 caregiver participants will be asked to join the focus groups, caregiver participants will be asked in sequential order should any of the initial 10 decline focus group participation. These focus groups will provide feedback needed to refine the intervention to specific needs of caregivers in rural Appalachia. The focus groups will be conducted over Zoom video conferencing and audio recorded using Zoom platform and automatically transcribed through Zoom. One focus group will be held pre intervention and the second will focus group will be held post intervention with the first ten caregiver participants willing to participate. These sessions will last approximately 90 minutes.

The following tasks will be associated with participation in this study and will take place at the person with dementia's home using Zoom video conferencing on the Zoom platform and saved on a UK-created share drive supported by Sanders-Brown Center on Aging. The zoom videos will be recorded and transcribed using Zoom platform. Informed consent will be obtained prior to the following research procedures. Caregiver participants will be asked to use their own personal devices if zoom capable. iPads with cellular service will be provided if the participants do not have a zoom-capable device or if they request to use an UK-issued iPad.

Visit 1: A screening visit will take place and will include review and obtaining informed consent for study participation following review of inclusion/exclusion criteria. Following consent completion, the screener will review demographic information and mail or email you a survey containing the following questions: Adult Sensory Profile; 20-Item Center of Epidemiology Depression Scale; UCLA Loneliness Scale; CHAMPS Social Engagement Scale; and the Zarit Caregiver Burden. Additionally, the screener will ship the behavior journal and iPad (if needed) via Fedex following the screening visit. Upon receipt, written instructions will direct you on how to use Zoom, behavior journals, and iPad (if used). The study coordinator will provide additional direction and confirm understanding of use at the baseline visit.

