Visit 2: Baseline data will be collected at Visit 2 consisting of seven surveys/questionnaires completed during the visit with the study coordinator: the Revised Memory and Behavior Problem Checklist, Adult Sensory Profile, Canadian Occupational Performance Measure, 6-Item Revised Caregiver Appraisal Scale; 6-Item Activities of Daily Living; 8-Item Instrumental Activities of Daily Living, Pearlin Mastery assessment, Stait-Trail Anxiety Scale, and Perceived Stress Scale. . The Situational Assessment Activity and Function Profile will be emailed or mailed to you for completion, as well. A focus group will also be held with selected participants. All intervention materials will be mailed to the patient's home following visit 2. Intervention materials will include items which offer environmental modifications to the home, for example:

Visit 3: The Occupational Therapist will meet with you for Visit 3. This will initiate week 1 in the behavior workbook. During this visit, the therapist will complete the Canadian Occupational Performance Measure, the Home Occupational Environment Assessment, and the Situational Assessment of the Home Environment.

Visit 4-8: At the end of each week, you and the patient you care for will meet with an occupational therapist to complete intervention training, as well as review the behavior journal and adverse events. These visits will last approximately one hour.

Visit 9: At the final week of intervention, you will engage in a two-hour session which will involve of adverse events, and completion of the Revised Memory and Behavior Problem Checklist, CES Depression scale; 6-Item Revised Caregiver Appraisal Scale; 6-Item Activities of Daily Living; 8-Item Instrumental Activities of Daily Living; Canadian Occupational Performance Measure, Stait-Trait Anxiety Scale; Zarit Caregiver Burden Scale, Pearlin Mastery assessment and Perceived Stress Scale surveys/questionnaires. A focus group will also be held with selected participants. The focus group will consist of the first ten participants willing to participate. The focus group will last approximately 60 minutes and will be conducted over zoom. The focus group will provide feedback needed to refine the intervention to specific needs of caregivers in rural Appalachia.

Visit 10: Four weeks following completion of the intervention, you will complete a follow up session consisting of the same visit 9 assessments.

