Existing PHI records will including: Name, email address, phone number, DOB, address, medical history, diagnoses, medications, primary contact information, University of Kentucky Healthcare medical identification number, tests completed at Sanders-Brown Center on Aging or the Kentucky Neuroscience Institute.

Sources of the PHI will come from the Sanders-Brown Center on Aging cohort database and clinical notes in patient files; and PHI from KNI will be collected through AEHR UKHC or Epic for any patients with memory impairment at KNI

Video recordings of all study sessions and audio recordings of focus groups will be collected using Zoom video conferencing. The automatic transcription feature will be used from Zoom platform.

If caregiver participants do not have a zoom capable device or if they request, a UK owned iPad equipped with vic plans will be mailed to caregiver participants for use during all study sessions. These devices will be mailed directly to participants homes via fedex and returned via Fedex using home pickup option.

66767

Behavior Workbook/Journals will be used to collect daily/weekly records of patient behaviors as observed and reported by caregivers. These will be printed and mailed to participants, and returned with iPads (if used) at conclusion of study.

Assessments (attached) used for data collection include:

6-Item Activities of Daily Living: Caregiver report of patient abilities for activities of daily living.

Adult Sensory Profile (ASP): A questionnaire to be completed by the caregiver regarding the patients' preferences and behaviors associated with environmental stimulation. Will be mailed or emailed for completion.

Canadian Occupational Performance Measure (COPM): An interview-based assessment with the caregiver regarding the patient's daily functional performance (i.e., bathing, dressing, feeding) and the caregiver's satisfaction with the level of performance.

20-Item Center of Epidemiology Depression Scale: Assessment of caregiver depressive symptoms.

CHAMPS Social Engagement Scale: Assessment of social engagement of caregivers.

Home Occupational Environment Assessment (HOEA): An assessment of home accessibility and safety.

8-Item Instrumental Activities of Daily Living: Caregiver report of patient abilities in instrumental activities of daily living, such as finance management and medication management.

Pearlin Mastery: Assessment on caregiver competence.

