4	DataCollection	HARMONY AT HOME PARTICIPANT MANUAL 1-16-22.docx	Clean Behavior Workbook 1-19- 22	0.228	[name]	1/19/2022 3:37:58 PM
4	DataCollection	HARMONY AT HOME PARTICIPANT WORKBOOK highlighted 1-19-22.docx	Highlighted Behavior Workbook changes	0.249	[name]	1/19/2022 3:37:05 PM
4	DataCollection	SAAF.pdf	SAAF updated form 1/2022	0.115	[name]	1/16/2022 3:48:53 PM
4	DataCollection	HARMONY AT HOME PARTICIPANT MANUAL 1-16-22.pdf	Behavior workbook revised 1/2022	0.465	[name]	1/16/2022 3:47:36 PM

						66767
4	AdditionInfoConsiderations	Signed_ Exemption Certification	IRB	0.268	(CLOSED
4	AdditionInfoConsiderations	Letter.pdf RE_ IIA form.pdf	Exemption form email from ORI reliance team to PI regarding	0.464	[name]	1:45:12 PM 1/5/2022 1:09:36 PM
4	AdditionInfoConsiderations	L HRP Training.pdf	HSP Training	0.679	[name]	12/13/2021 11:40:53 AM
4	AdditionInfoConsiderations	IIA for - 66767.pdf		0.408	[name]	12/12/2021 6:13:35 PM
4	AdditionInfoConsiderations	IRB Determination.pdf	Consultant Documentation	0.114	[name]	12/12/2021 6:13:15 PM
4	Informed ConsentParental Permission	Consent CAREGIVER clean 12-12.pdf	Caregiver consent clean	0.205	[name]	12/12/2021 6:11:18 PM
4	DataCollection	UCLA remote.pdf	UCLA Loneliness	0.081	[name]	11/12/2021 3:58:13 PM
4	DataCollection	CHAMPS remote.pdf	Social Engagement Scale	0.145	[name]	11/12/2021 3:58:00 PM
4	DataCollection	SAHE 11-12-21.doc	Situational Assessment Home Environment	0.117	[name]	11/12/2021 3:45:15 PM
4	DataCollection	Center For Epidemiologic Studies Scale.pdf	CED S	0.041	[name]	11/12/2021 3:28:49 PM
4	DataCollection	Demographic Caregiving History.pdf	Demographic Info	0.047	[name]	11/12/2021 3:28:18 PM
4	DataCollection	State Trait Y1.pdf	State Trait	0.038	[name]	11/12/2021 3:27:22 PM
4	DataCollection	RCAS.pdf	Caregiver appraisal scale	0.041	[name]	11/12/2021 3:11:25 PM
4	DataCollection	katz-adl.pdf	ADL Assessment	0.086	[name]	11/12/2021 3:10:31 PM
4	DataCollection	lawton-iadl.pdf	IADL assessment	0.080	[name]	11/12/2021 3:10:11 PM
4	ResearchProcedures	Caregiver schedule of events 11-12.pdf	Schedule of Events	0.071	[name]	11/12/2021 3:02:44 PM
4	AdditionInfoConsiderations	3.3 DSMP10-4-21.docx	DSMP Clean	1.099	[name]	10/4/2021 7:34:28 PM
4	AdditionInfoConsiderations	DMSP Revised highlighted.docx	DSMP revised with track changes	1.377	[name]	10/1/2021 2:00:10 PM
4	Waiver	WoA Approval Letter - IRB# 66767.pdf	Waiver of authorization approval letter	0.204	[name]	8/23/2021 4:50:48 PM

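### The behavior workbook is sent out before the baseline questionnaires, so in this one-arm study the baseline for the change scores is not protected from early exposure to program material

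*Combined protocol and SAP*

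**What the plan says.** The Study Design section states: "This study will utilize a one-arm, pre/post design". Four places in the protocol then set the timing.

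- **Research Procedures, Visit 1 (screening).** After this visit "the screener will ship the behavior journal and iPad (if needed) via Fedex following the screening visit". Written directions for the journal come with the shipment, and "The study coordinator will provide additional direction and confirm understanding of use at the baseline visit".
- **Research Procedures, Visit 2 (baseline).** The Pearlin mastery, RMBPC, Perceived Stress and Caregiver Appraisal scales are completed with the coordinator. The same paragraph says "All intervention materials will be mailed to the" patient's home once Visit 2 is over. It describes these materials as items for modifying the home environment. The Resources section gives the same timing for the toolboxes.
- **Research Procedures, Visit 3.** The occupational therapist starts the program: "This will initiate week 1 in the behavior workbook".
- **Data Collection & Research Materials.** Journal and workbook are named together: "Behavior Workbook/Journals will be used to collect daily/weekly records of patient behaviors as observed and reported by caregivers".

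In the list of submitted documents at the end of the file, the PDF named Participant Manual, dated 1-16-22, carries the description "Behavior workbook revised 1/2022".

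**The concern.** A one-arm study has no concurrent group to absorb whatever happens before baseline. The SAP tests whether the mean response differs among three visits, so each change score depends on the first measurement being taken before the program begins.

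The plan holds back the environmental materials until after Visit 2, which protects the baseline. It does not do the same for the workbook. A caregiver may read the workbook, or begin noting behaviors, before answering the mastery and RMBPC questions. If the workbook contains training content, the baseline would then be partly a treated measurement. Exposure could also differ between dyads, depending on when the parcel arrives and whether it is opened.

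**Working it through.** The point rests on the order of events. The plan's only power statement concerns the adherence rate against 60% with 40 caregivers. It is not an input here, so there is no stated figure to reproduce.

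**Sequence as written**

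1. After Visit 1, the journal is shipped with written directions.
2. At Visit 2, the coordinator adds direction on the journal and the baseline scales are completed. The order within the visit is not stated.
3. After Visit 2, the environmental materials are mailed.
4. At Visit 3, workbook week 1 begins.
5. At Visits 4 to 8, the therapist reviews the journal. The 42 hours budgeted for intervention and journal work fall within the six-week intervention.

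**What can come before the baseline scales**

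- The written directions are clearly sent before Visit 2.
- Reading the workbook is possible; no sentence excludes it.
- The coordinator's explanation may come before or after the questionnaires.
- Making entries is not scheduled before Visit 3, but it is not barred either.
- The Zarit and depression scales are sent out after Visit 1 with no completion date, so their order relative to the journal is also open.

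The text sets no interval between Visits 1 and 2. A caregiver schedule of events is listed as an attachment but is not reproduced, so the interval may be given there.

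**Is the journal program material?** The Data Collection section treats workbook and journal as one item, and the document list applies the workbook description to the file named Participant Manual. The list also has a Participant Workbook file described as the highlighted workbook changes. Manual and workbook therefore look like names for one item. The names do not show what it contains.

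**Illustration of size (assumed values)**

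Inputs: n = 40 caregivers, or 75% of 40 = 30 at the retention target; alpha = 0.74 for the mastery subscale (Data Collection section), used as a stand-in for the pre/post correlation; an assumed baseline shift of 0.1 to 0.2 SD.

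- SD of change = √(2 × (1 − 0.74)) = √0.52 = 0.72 SD
- n = 40: SE = 0.72/√40 = 0.114 SD; 0.1/0.114 = 0.9 and 0.2/0.114 = 1.8 SE
- n = 30: SE = 0.72/√30 = 0.132 SD; 0.1/0.132 = 0.8 and 0.2/0.132 = 1.5 SE

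Alpha measures internal consistency, not test-retest correlation. A lower correlation gives a larger SD of change and so a smaller ratio.

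A second view uses a paired t-test (two-sided 0.05), with effects now in units of the SD of change. The change detectable with 80% power is 0.45 at n = 40 and 0.53 at n = 30. If early exposure moved baseline toward the post-test value by 0.10 or 0.20 of those units, power would fall to 59% or 35% at n = 40, and to 62% or 41% at n = 30. The documents give no evidence that a shift of this size, or any shift, occurs.

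**The case against.** The strongest reply is that the journal is a data-collection form. It is described under data collection and filed in that category, and its use starts at Visit 3. Much of this stands, and it rules out several stronger readings that a reader might infer.

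- **That the two shipping rules contradict each other.** They do not. The materials held back are described as environmental items and toolboxes, and no sentence classes the journal among them.
- **That recording starts before baseline.** No entry is scheduled before week 1.
- **That all 40 caregivers have a biased baseline.** The schedule exposes all of them to the possibility. It does not show that any of them read or used the workbook early.
- **That the program's core skill is rehearsed early.** The intervention description is about assessing and modifying environmental antecedents in therapist-led training. It does not say that recording behavior is the skill taught, and the list of skills is missing from the public text.
- **That the RMBPC fall is exaggerated.** More noticing at baseline would push that way. But journaling runs through the intervention, so noticing may be raised at post-test as well, and early exposure could make the two occasions more alike. For mastery, a higher baseline would hide benefit. The direction is open.
- **That the feasibility conclusions are compromised.** Retention and adherence are judged against fixed 75% and 60% thresholds, not against baseline.

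It can also be said that a baseline taken before any journaling differs in observer practice from a post-test taken after six weeks of it. That difference is already built into the plan, since journaling is meant to start at Visit 3. Later shipment only makes it uniform across dyads.

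What remains is narrow: directions go out before baseline, the order of explanation and questionnaires is unspecified, and no rule prevents early reading or use.

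**Conclusion.** The concern holds as a gap in protection, not as an established bias. It applies to the change scores for mastery, RMBPC, stress and appraisal, for which the Visit 2 value is the only comparator. The conclusion rests on the visit text and on reading workbook, journal and manual as one item, as the document list suggests. Whether that item contains training content cannot be checked. The size is therefore unknown, and the standard-error and power figures show only what an assumed shift would mean. Severity is minor. It is still worth acting on, because a better-protected schedule is available at almost no cost.

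**What to change.** **Schedule**

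- After Visit 1, ship only the iPad and the Zoom instructions, where needed.
- Put the behavior workbook/journal in the parcel already mailed after Visit 2.
- Give the journal instruction once the Visit 2 questionnaires are complete, or at Visit 3.

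**Dyads already enrolled.** The file is stamped closed and the SAP is written in the past tense, so the schedule change may serve only a later study. For this one, where dates exist, record whether the workbook was received or used before the Visit 2 questionnaires, and show the mastery and RMBPC changes by that status. If there are no dates, or every dyad falls in one group, state it as a limitation. In either case, say whether the workbook contains training content.

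**Cost.** About two sentences in the visit schedule and no additional shipment. The downside is a few minutes of instruction moved later. Visit 3 already carries three assessments, so the end of Visit 2 may be the easier place.
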